5.2 Exclusion Criteria

Patients meeting any of the following are ineligible to participate in this study:

1. Patients with any active autoimmune diseases or a history of autoimmune diseases (including but not limited to the following: autoimmune hepatitis, interstitial pneumonitis, uveitis, enteritis, hepatitis, hypophysitis, vasculitis, nephritis, hyperthyroidism, hypothyroidism; adults with vitiligo or completely relieved childhood asthma can be enrolled if they do not require any intervention; patients with asthma requiring medical intervention with bronchodilators cannot be enrolled);

2. Patients who are currently using immunosuppressive agents, or systemic or absorbable local hormonal therapies for immunosuppression purposes (> 10 mg/day prednisone or equivalent) and still use the above drugs within 2 weeks prior to enrollment;
3. Patients who have experienced severe allergic reactions to other monoclonal antibodies;
4. Patients with untreated metastases to central nervous system. Patients who have received treatment for brain or meningeal metastasis can be included if they are clinically stable (MRI) for at least 1 month and have stopped systemic hormonal therapy (> 10 mg/day prednisone or equivalent) for more than 2 weeks;
5. Imaging (CT or MRI) results show that the tumor has invaded the large blood vessels or has an unclear boundary with the blood vessels;
6. Imaging (CT or MRI) results show significant cavitation or necrosis of lung tumors;
Patients with marginal adenocarcinoma with cavity may be enrolled after discussion with the leading site.
7. Patients with hypertension which cannot be well controlled by antihypertensives (systolic pressure ≥ 140 mmHg or diastolic pressure ≥ 90 mmHg);
8. Patients with clinical symptoms or diseases of the heart that are not well controlled, such as (1) $>$ NYHA Class II cardiac failure; (2) unstable angina; (3) myocardial infarct within past 1 year; (4) clinically significant supraventricular or ventricular arrhythmia requiring treatment or intervention;
9. Patients with abnormal coagulation functions (PT > 16 s, APTT > 43 s, TT > 21 s, Fbg < 2 g/L) and hemorrhagic diathesis or those who are currently treated by a thrombolytic or anticoagulant therapy;
10. Patients with urinalysis results indicating that the urine protein is $\geq ++$ and the quantitative test of urine protein confirms that the 24-hour urine protein is > 1.0 g;
11. Patients who have previously received radiotherapy, chemotherapy or surgery that is less than 4 weeks before the study after the end of such treatments (last dose), or patients whose last dose of oral targeted drugs is less than 5 drug half-lives; Patients with adverse events caused by the previous treatment (except for alopecia) that have not returned to CTCAE Grade ≤ 1 ;
12. Patients with clinically symptomatic ascites or pleural effusion requiring therapeutic paracentesis or drainage;

13. Patients with obvious hemoptysis or a daily amount of hemoptysis of half a teaspoon (2.5 mL) or more within 2 months before randomization;
14. Patients with clinically significant hemorrhage symptoms or a clear hemorrhagic diathesis within 3 months prior to randomization, such as hemorrhage of digestive tract, stomach ulcer with hemorrhage, baseline fecal occult blood ++ or above, or vasculitis;
15. Had events of arterial/venous thrombosis within 6 months prior to randomization, such as cerebrovascular accidents (including transient ischemic attacks, cerebral hemorrhage, and brain infarction), deep vein thrombosis, and pulmonary embolism;
16. Known hereditary or acquired hemorrhage and thrombophilia (such as hemophilia, coagulopathy, thrombocytopenia, hypersplenism, etc.);
17. Patients with active infection or unexplained fever of $> 38.5^{\circ}\text{C}$ during screening or prior to the first dose;
18. Patients with previous or current objective evidence of pulmonary fibrosis, interstitial pneumonia, pneumoconiosis, radiation pneumonitis, drug-induced pneumonitis, and severe lung function impairment;
19. Subjects with congenital or acquired immunodeficiency (such as HIV infection), or active hepatitis (hepatitis B: HBsAg positive and HBV DNA $>$ upper limit of normal; hepatitis C: HCV antibody positive and HCV virus titer $>$ upper limit of normal);
20. Those who have used study drugs of other clinical trials within 4 weeks before the first dose of this study;
21. Patients with previous or concurrent malignancies at other sites (except for cured skin basal cell carcinoma and cervical carcinoma in situ);
22. Patients who may receive other systemic anti-tumor treatments during the study;
23. Patients with bone metastasis who have received a palliative radiotherapy in an area of $> 5\%$ of bone marrow area within 4 weeks prior to the participation in this study;
24. Patients who have previously received other anti-PD-1 antibody treatments or other immunotherapies targeting PD-1/PD-L1;
25. Patients who have received live vaccines within less than 4 weeks before the first dose or may receive live vaccines during the study;

26. Patients who may have other factors leading to the discontinuation of the study as judged by the investigator, such as other serious diseases (including mental illness) requiring concomitant treatment, serious laboratory test abnormalities, or accompanied by family or social factors that can affect the safety of the subject or the collection of data and samples.

5.3 Subject's Withdrawal

5.3.1 Criteria for withdrawal/treatment discontinuation

1. The subject withdraws informed consent and requests to withdraw from the study;
2. Imaging examinations show progressive disease;

Upon the first discovery of progressive disease by imaging examinations, it must be confirmed after 4 weeks (except for rapid progression and significant clinical progression);

If a subject shows local progression (1 to 4 lesions show progress) but the clinical symptoms are stable, the treatment can be continued according to the judgment of the investigator until imaging examinations show progressive disease again.

Definition of clinically stable: a. no clinically significant symptoms or changes in laboratory tests; b. no changes in the performance status score (deterioration); and c. non-tumor rapid progression and tumor progression not involving major organs/sites (e.g., spinal cord compression).

3. Treated by SHR-1210 for 2 years (no progressive disease as shown by imaging);
4. Subjects with intolerable toxicity;
5. Subjects with poor compliance;
6. Subjects lost to follow-ups or show positive blood HCG results;
7. Other reasons for which the investigator considers withdrawal as necessary.

Note: Subjects with radiologically confirmed PD may continue the study drug after providing informed consent for continuation after PD, if they are judged able to benefit from the study drug by the investigator. The treatment may continue until another radiographic PD or they can no longer benefit from the treatment. Subjects who continue the medication after PD will undergo periodic visits and efficacy evaluations according to the visit procedures specified in the protocol.

Subjects who agree to continue the treatment after PD should be fully informed of possible alternative treatments, potential risks of continuation, etc.

5.3.2 Handling of withdrawn subjects

The efficacy and safety investigations to be completed upon study withdrawal as specified in the protocol must be completed as much as possible. In addition, the safety follow-up should be completed along with fully collected AEs and their outcomes. The survival follow-up should be completed to record subsequent treatment regimens and the survival status of the subjects. The investigator can recommend or provide new or alternative treatments to a subject based on the condition of the subject. Patients showing no progressive disease need to be continuously followed-up for imaging evaluation until the patients begin a new treatment or show progressive disease

5.4 End of Study

Stage I:

The Stage I of this study will end at 3 months after the last dose of the last subject in the tolerability observation period if subjects in the PK expansion stage complete the specified PK blood sampling;

Stage II:

At 6 months after the first dose of the last subject in Stage II, the primary and secondary endpoints will be statistically analyzed.

All subjects will be followed up until 12 to 24 months after the last dose of the last subject, and supplemental analysis of the primary and secondary endpoints will be performed thereafter.

After the end of the study, if the subjects may continue to benefit from the study drug, the medication may be continued until a criterion for discontinuation is met. The occurrence of SAEs will be collected and recorded during the treatment and after the last dose according to the protocol.

5.5 Termination Criteria

1. Discovery of unexpected, important, or unacceptable risks to the subjects;
2. Major errors in the protocol found during the implementation of the study;
3. Ineffective study drug/treatment, or meaninglessness to continue the study;
4. Extreme difficulties in completing the study due to reasons such as severe delays in subject recruitment or frequent protocol deviations.

6 STUDY DRUGS

6.1 Overview of Study Drugs

6.1.1 Drug information

- **SHR-1210:**

Name: SHR-1210 for injection

Manufacturer: Shanghai Hengrui Pharmaceutical Co., Ltd./Suzhou Suncadia Biopharmaceuticals Co., Ltd.

Dosage Form: Lyophilized powder for injection

Route of Administration: Intravenous injection

Strength: 200 mg/20 mL vial.

Storage and stability: Placed in a 2-8 °C medical refrigerator during storage and the shelf life is tentatively set to 2 years. Do not freeze.

- **Apatinib:**

Name: Apatinib Mesylate Tablets (Apatinib)

Manufacturer: Jiangsu Hengrui Pharmaceuticals Co., Ltd.

Dosage Form: Tablets

Route of Administration: Oral

Strength: 250 mg/tablet; 375 mg/tablet

Storage and Stability: Away from light, sealed, stored at below 25 °C. Valid for 2 years.

6.1.2 Drug packaging and labeling

Specification and packaging of SHR-1210: 200 mg/20 mL vial, one vial per box, and 20 boxes per carton.

SHR-1210 drug label (for illustration only and the actual label shall prevail), the drug number is increased incrementally from 0001.

Small Box Label			Vial Label		
SHR-1210 for Injection	Clinical Study Approval No.: 2016L01455	Strength: 200 mg/vial	SHR-1210 for Injection	Clinical Study Approval No.: 2016L01455	Strength: 200 mg/vial
For Clinical Study Use Only			For Clinical Study Use Only		
Study Name: A Phase II Clinical Study of Anti-PD-1 Antibody SHR-1210 Combined with Apatinib Mesylate in the Treatment of Advanced Non-Small Cell Lung Cancer Study No.: SHR-1210-APTN-II-202-NSCLC Dosage Form: Lyophilized powder Study Center: Shanghai Pulmonary Hospital, Tongji University Usage: 200 mg, Q2W, IVGTT. Note: Prepare as per study protocol. Drug No. _____ Quantity: 1 vial/box Storage Method: Store at 2-8 °C away from light Batch No.: _____ Expiry Date: DD/MM/20YY Sponsor: Jiangsu Hengrui Pharmaceuticals Co., Ltd.			Study Name: A Phase II Clinical Study of Anti-PD-1 Antibody SHR-1210 Combined with Apatinib Mesylate in the Treatment of Advanced Non-Small Cell Lung Cancer Study No.: SHR-1210-APTN-II-202-NSCLC Dosage Form: Lyophilized powder Study Center: Shanghai Pulmonary Hospital, Tongji University Usage: 200 mg, Q2W, IVGTT. Note: Prepare as per study protocol. Drug No. _____ Preparation Date: ____/____/____ Storage Method: Store at 2-8 °C away from light Batch No.: _____ Expiry Date: DD/MM/20YY Sponsor: Jiangsu Hengrui Pharmaceuticals Co., Ltd.		

Big Box Label		
SHR-1210 for injection	Clinical study approval No.: 2016L01455	Strength: 200 mg/vial
For Clinical Study Use Only		
Study Name: A Phase II Clinical Study of Anti-PD-1 Antibody SHR-1210 Combined with Apatinib Mesylate in the Treatment of Advanced Non-Small Cell Lung Cancer Study No.: SHR-1210-APTN-II-202-NSCLC Dosage Form: Lyophilized powder, 200 mg/vial Study Center: Shanghai Pulmonary Hospital, Tongji University Usage: 200 mg, Q2W, IVGTT. Note: Prepare as per study protocol. Quantity: 20 vials per box Storage Method: Store at 2-8 °C away from light Batch No.: _____ Expiry Date: DD/MM/20YY Sponsor: Jiangsu Hengrui Pharmaceuticals Co., Ltd. Manufacturer: Shanghai Hengrui Pharmaceutical Co., Ltd.		

Packaging specifications and quantity of apatinib:

The label content includes:

Label name: Drugs to be used in the phase II clinical study of anti-PD-1 antibody SHR-1210 combined with apatinib mesylate in the treatment of advanced non-small cell lung cancer

Strength: 250mg/tablet or 375 mg/tablet

Indication: For the treatment of advanced non-small cell lung cancer

Usage: 1 tablet per day (250 mg/d and 375 mg/d dose groups); 2 tablets per day (500 mg/d dose group), once a day taken orally after meal

Drug number, storage conditions, batch number, expiration date, study site (Jiangsu Hengrui Pharmaceuticals Co., Ltd.)

Precautions: For clinical use only; please return the remaining drug to the physician

The drug is packaged in aluminum-plastic blister packs with 10 tablets per pack, and each small box contains 3 or 6 packs.

6.2 Preparation of SHR-1210

SHR-1210 is a lyophilized powder for injection, which needs to be formulated before intravenous drip (see the pharmacy manual of SHR-1210 for details).

Since this product does not contain preservatives, please perform aseptic operations when formulating the drug preparation.

- Each vial of lyophilized powder is quantitatively reconstituted in 5 mL of distilled water for injection. During the operation, the distilled water is slowly added into the vial along the vial wall. Please do not directly drop the distilled water onto the surface of the lyophilized powder (the post-reconstitution concentration is 40 mg/mL)
- Do not vigorously shake the vial during reconstitution. Instead, reconstitute the powder in a gentle way with slow vortex. After reconstitution, allow the vial to stand for 6 min to allow the foam to disappear.
- Visually observe the solution after reconstitution to see whether there are particles and discoloration. After reconstitution, the liquid should be colorless or slightly yellowish. There may be a small number of light-gray small particles falling into the vial due to the puncture of vial stopper by the needle. However, these particles will be filtered by the 0.2 μ M filter attached to the infusion set and hence will not affect the subsequent use of the drug solution. If there are other particles other than the ones mentioned above, please do not continue to use this vial of drug.
- Draw a corresponding volume of the reconstituted solution from the vial and dilute it in 100 mL of 5% glucose for injection or 0.9% sodium chloride for injection. Avoid generating a large number of air bubbles during the dilution process. After dilution, slowly invert the infusion bag several times to mix well. Maintain the final concentration at between 0.5 mg/mL and 10 mg/mL.
- Within 2 h after the dilution is completed, use an infusion set equipped with an in-line filter (0.2 μ M) to finish the injection via intravenous drip. After the drug injection is completed, use about 20 mL of 5% glucose for injection to flush the remaining drug in the infusion line into the body. Do not use this infusion line to administer other drugs. Each infusion takes 30 min (not less than 20 min, no more than 60 min) (including the final rinse stage).

6.3 Administration Regimen

SHR-1210 will be administered via intravenous drip (without prophylaxis) with a fixed dose of 200 mg within 30 min (not less than 20 min, no more than 60 min), once every 2 weeks. Each cycle contains 4 weeks (the subjects for the expanded PK study will receive one dose on D1 of Cycle 1 of the study) and the longest period of drug use is 2 years.

Apatinib will be orally administered after meals (the subjects for the expanded PK study will receive the drug orally under fasting on Day 28 of Cycle 1 and Day 28 of Cycle 2), once a day, and one tablet (250 mg/tablet or 375mg/tablet) or 2 tablets (250 mg/tablet, 500 mg dose group) each time. The drug administration will be continued through the study.

Subjects enrolled for the study in the tolerability observation stage and subjects enrolled for the Stage II of the study will be given SHR-1210 on D1 and D15 of each cycle from the beginning of treatment; apatinib will be given via oral administration once daily.

Subjects enrolled for the expanded PK study will be given SHR-1210 on D1 in Cycle 1 and on D1 and D15 in each cycle starting from Cycle 2. These subjects will also be given daily oral administration of apatinib continuously starting from D22 in Cycle 1.

Definition of postprandial administration: administration within 30 min after the end of a meal.

The subjects will continue to use the study drugs until the criteria for treatment discontinuation specified in the protocol are met.

6.4 Dose Modification

The study treatment may be modified according to the toxic side effects appeared. The options for treatment modification include: interruption, dose reduction, change in method of administration, and discontinuation;

In this study, only interruptions for up to 12 weeks are permitted for SHR-1210 treatment; A SHR-1210 dose delayed by more than 3 days shall be skipped, and the administration may be resumed at 200 mg at the next scheduled time point.

Dose modifications caused by apatinib-related toxicity include: dose interruption, dose reduction (500 mg/d or 375 mg/d dose groups), change in method of administration (first modification: 5 days of drug administration followed by 2 days of dose interruption; re-modification: 1 day of drug administration followed by 1 day of dose interruption), and discontinuation. Further adjustments will not be allowed after the dose or method of administration of apatinib is modified during the study period, unless such adjustments are agreed upon by the investigator and the sponsor after discussion.

In the event of an apatinib-related adverse reaction, the dose should be interrupted first. After the toxicity has returned to an acceptable level, the following options may be selected as appropriate: resume administration using the original dose, reduce the dose, modify the method of administration or discontinue the drug. Subjects may continue SHR-1210 as monotherapy if apatinib treatment is discontinued.

For immune-related toxicity occurring during the study, such as immune-related pneumonitis, hepatitis and colitis, the administration of SHR-1210 and apatinib should be interrupted as appropriate. The administration can be resumed when the toxicity returns to Grade ≤ 1 or baseline levels (for subjects with abnormal laboratory parameters such as ALT/AST and TBIL at baseline). The administration of SHR-1210 should be resumed first. The administration of apatinib can be resumed when no significant abnormality is observed within 7 to 14 days after SHR-1210 administration. The route of subsequent administration of apatinib should be modified.

Rules for Dose Modifications

Treatment-Related Toxicity		Grade	Whether to Interrupt Treatment		Criteria for Resuming	Dose Modification Method	Criteria for Discontinuation
			SHR-1210	Apatinib			
Toxicity related to SHR-1210 and apatinib	Hematologic toxicity (except for decreased lymphocyte count)	Grade 1-2	No	No	—	—	—
		Grade 3	No	Yes	Until the toxicity returns to Grade ≤ 2	Resume at original dose	Two episodes of Grade 4 hematological toxicity
		Grade 4	Yes	Yes	Until the toxicity returns to Grade ≤ 2	Dose reduction or modification of method of administration	
	Non-hematologic toxicity	Grade 1	No	No	—	—	—
		Grade 2 (last for ≥ 7 d)	Yes	Yes	Until the toxicity returns to Grade ≤ 1	Resume at original dose	SHR-1210 interruption for more than 12 weeks
		Grade 3	Yes	Yes	Until the toxicity returns to Grade ≤ 1	Dose reduction or modification of method of administration	
Toxicity related to SHR-1210	Reactive capillary endothelial proliferation	Grade 3	Yes	No	Until the toxicity returns to Grade ≤ 2	Resume at original dose	SHR-1210 interruption for more than 12 weeks

Treatment-Related Toxicity		Grade	Whether to Interrupt Treatment		Criteria for Resuming	Dose Modification Method	Criteria for Discontinuation
			SHR-1210	Apatinib			
Apatinib-Related Toxicities	Hypertension	Grade 3 (after corrective treatment)	No	Yes	Wait until blood pressure returns to within 140/90 mmHg	Dose reduction or modification of method of administration	Subjects with persistent Grade 3 hypertension after the best corrective treatment and the modification of method of administration of apatinib
	Proteinuria (without significant increase in blood creatinine)	Grade 3 (24 h urine protein quantification)	No	Yes	Until the toxicity returns to Grade ≤ 2	Dose reduction or modification of method of administration	Subjects with persistent Grade 3 proteinuria after the best corrective treatment and the modification of method of administration of apatinib
	Hand-and-foot syndrome	Grade 3	No	Yes	Until the toxicity returns to Grade ≤ 1	Dose reduction or modification of method of administration	Subjects with persistent Grade 3 hand-and-foot syndrome after the best corrective treatment and the modification of method of administration of apatinib
	Headache	Grade 2 (last for ≥ 7 d) or Grade 3	No	Yes	Until the toxicity returns to Grade ≤ 1	Dose reduction or modification of method of administration	Apatinib interruption for more than 28 days

The investigator may consider interrupting the treatment for subjects who experience significant toxicity during the study, such as Grade 3 or greater treatment-related toxicity, or Grade 2 non-hematological toxicity lasting for 2 weeks and longer (except for asymptomatic Grade 2 hypertension), abnormal laboratory findings (except < 2 g/24 h proteinuria). After the toxicity resolves, the dose of apatinib should be reduced or the method of apatinib administration should be adjusted accordingly.

In the course of the study and based on the above regulations for dose modification, the investigator may modify the dose appropriately by comprehensively considering the treatment-related toxicity in the subjects (if a subject experiences multiple Grade 2 treatment-related toxicities and shows poor tolerance to the study drug, the dose of apatinib can be reduced or the administration of apatinib can be maintained at the original dose by given intermittently with observation after treatment delay and recovery from toxicity).

During the study, if a subject has fever ($> 38^{\circ}\text{C}$) and needs to use medications for corrective treatment; in the case of obvious wheezing, polypnea, symptoms of suffocation or rash, the administration of SHR-1210 should be skipped for the current or next scheduled time of SHR-1210 administration before the symptoms are recovered. After the symptoms are relieved and become stable for more than 7 days, the subjects can be given SHR-1210 according to the subsequent administration schedule. For subjects with fever and wheezing, the possibility of pneumonitis should be ruled out by imaging examinations before drug administration if necessary.

In the case of hypertensive crisis, cerebral hemorrhage, Grade ≥ 2 pulmonary hemorrhage, other Grade ≥ 3 hemorrhage, arterial thrombosis, Grade 4 venous thrombosis, leukoencephalopathy syndrome, or gastrointestinal perforation, apatinib should be discontinued, SHR-1210 should be interrupted and active symptomatic treatment should be given. The resumption of SHR-1210 treatment shall depend on the toxicity recovery.

During the study, in the case of Grade ≥ 3 immune-related pneumonitis, Grade ≥ 3 TBIL elevation (recurrent), Grade 4 ALT/AST elevation (recurrent), other Grade 4 immune-related toxicities (except for hypothyroidism), Grade 4 injection reactions, or the interruption of SHR-1210 administration for more than 12 weeks due to immune-related toxicity but the toxicity is still unable to return to Grade ≤ 1 or baseline levels (subjects with baseline abnormality), SHR-1210 should be permanently discontinued.

After discontinuation of SHR-1210 treatment, subjects may continue to receive apatinib monotherapy after toxicity recovery if the investigator judges that the subjects can benefit from the apatinib monotherapy, until an event meeting the criteria for discontinuation as specified in the protocol occurs.

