3.1.1 Definition of clinically significant toxicity

1. Grade 4 hematological toxicity or Grade ≥ 3 thrombocytopenia with hemorrhage, Grade ≥ 3 neutropenia with fever and infection;
2. Grade ≥ 3 non-hematological toxicity (except for abnormal laboratory test parameters), hypertension, rash, diarrhea, nausea, and vomiting that cannot be controlled after symptomatic treatment;
3. Grade ≥ 3 abnormal laboratory test parameters that lead to medical intervention, hospitalization, or lasting for ≥ 7 days;
4. SHR-1210 interruption for > 14 days due to relevant toxicity (delayed administration in Cycle 1 or Cycle 2);
5. Apatinib interruption for > 7 days due to relevant toxicity.

3.1.2 Definition of subjects with incomplete tolerance evaluation:

During the observation period of tolerability, the dose of SHR-1210 is < 90% of the prescribed dose due to non-clinically significant toxicity (such as injection reactions).

Subjects who do not complete the tolerability evaluation will not be included in the overall number of subjects undergoing tolerability evaluations, and each dose group is required to have ≥ 10 subjects for the tolerability observation.

Exemption: If ≥ 7 subjects in a dose group do not develop clinically significant toxicity during the tolerability observation period, the dose group is considered to be tolerable and no new subjects will be enrolled into this dose group.

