In the clinical study of SHR-1210, the monitoring of signs and symptoms of immune-related thyroid dysfunction in the subjects will be strengthened. A high-dose hormone therapy will be given to subjects with a Grade 3 or greater event, but subjects with a Grade 4 event should permanently discontinue SHR-1210.

- **Immune-related nephritis and renal failure**

In the clinical study of SHR-1210, the monitoring of signs and symptoms of immune-related nephritis in the subjects will be strengthened. A high-dose hormone therapy will be given to subjects with a Grade 2 or greater event. Subjects with a Grade 2 event can interrupt SHR-1210 and be treated, but subjects with a Grade 3 or 4 event should permanently discontinue SHR-1210.

● Immune-related hypophysitis

In the clinical study of SHR-1210, the monitoring of signs and symptoms of immune-related hypophysitis in the subjects will be strengthened. A high-dose hormone therapy will be given to subjects with a Grade 2 or greater event. Subjects with a Grade 2 or 3 event can interrupt SHR-1210 and be treated, but subjects with a Grade 4 event should permanently discontinue SHR-1210.

● Other immune-related adverse reactions

In principle, interruption of SHR-1210 is preferred based on the severity of the adverse reaction. The study treatment can be considered to resume when AE returns to Grade ≤ 1 . The study treatment should be permanently discontinued if severe (Grade 3) or life-threatening (Grade 4) adverse reactions occur.

The treatment of immune-related adverse reactions should be based on the medical practice and guidelines of the study center. The treatment recommendations for irAEs are shown in Table 8-2 for reference.

Table 8-2. Treatment recommendations for irAEs related to SHR-1210 for injection

CTCAE Grade	Clinical Management*	SHR-1210 Treatment
Grade 1 (mild)	
 - Close observation, especially for diarrhea • Supportive care 	Continue
Grade 2 (moderate)	
 - Closely monitoring • Supportive care • Local application of steroids, such as for dermatitis/colitis, etc. 
Symptoms persist for ≥ 7 days, start 1 mg/kg of prednisone or equivalent
 
Symptoms are aggravated, give intravenous or oral administration of 1 mg/kg prednisone
	Interrupt, resume when recovers to Grade ≤ 1
Grade ≥ 3 (severe)*	-2 mg/kg of prednisone or equivalent	Permanent discontinuation

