* The treatment may not be interrupted for Grade 3 local skin and endocrine disorders, because they can often heal (skin) or be treated using an alternative treatment (endocrine)

(Weber, [name], et al., "Toxicities of immunotherapy for the practitioner," J Clin Oncol, April 2015)

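### For rash, the Section 6.4 text, the Section 6.4 table and Table 8-2 give conflicting SHR-1210 instructions at Grades 1, 2 and 3, and no passage says which governs

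*Protocol*

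**What the plan says.** Four places in the protocol bear on SHR-1210 dosing when a subject has a rash.

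- **Section 6.4, text after the table.** After fever above 38 °C, the sentence continues "and needs to use medications for corrective treatment; in the case of obvious wheezing, polypnea" and ends "symptoms of suffocation or rash, the administration of SHR-1210 should be skipped for the current or next scheduled time of SHR-1210 administration". The restart condition is "After the symptoms are relieved and become stable for more than 7 days". No CTCAE grade and no causality condition is given.
- **Section 6.4, Rules for Dose Modifications table.** The rows under "Non-hematologic toxicity" cover treatment-related toxicity. At Grade 1 neither drug is interrupted. At Grade 2 both are interrupted if the event lasts at least 7 days, and there is no row for a shorter Grade 2 event. At Grade 3 both are interrupted. Treatment resumes at Grade 1 or below.
- **Section 8.7, Table 8-2.** This covers immune-related events and is described as being for reference. At Grade 1 the management starts with "Close observation, especially for diarrhea" and SHR-1210 continues. At Grade 2 it is interrupted until Grade 1 or below. At Grade 3 or above it is permanently discontinued. A footnote adds: "The treatment may not be interrupted for Grade 3 local skin and endocrine disorders, because they can often heal (skin").
- **Sections 8.7 and 9.1, other immune-related adverse reactions.** Grade 3 and Grade 4 reactions lead to permanent discontinuation.

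**The concern.** A site with a subject who has a rash on a dosing day needs one answer to three questions: whether to give SHR-1210, whether apatinib is held too, and when to restart. The protocol gives several, and two of them sit in the same section with equal standing.

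Subjects with the same event may therefore be managed differently between sites, which is a matter of subject protection. It also affects the data. SAP Section 5.4.3 tabulates adverse events leading to interruption and to discontinuation of SHR-1210, and Section 5.4.1 summarises SHR-1210 dose frequency intensity. If sites follow different passages, those summaries mix the tolerability of the combination with each site's choice of rule.

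**Working it through.** The plan states no figure to reproduce. The check is a side-by-side reading, followed by simple arithmetic on dosing.

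**SHR-1210 action for a treatment-related or immune-related rash**

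| Grade | 6.4 text | 6.4 table | Table 8-2 and related rules |
|---|---|---|---|
| 1 | Skip; restart after more than 7 stable days | Not interrupted | Continue |
| 2, under 7 days | Skip; same restart | No row | Interrupt; resume at Grade ≤ 1 |
| 2, 7 days or more | Skip; same restart | Interrupt both drugs; resume at Grade ≤ 1 | Interrupt; resume at Grade ≤ 1 |
| 3 | Skip; same restart | Interrupt both drugs; resume at Grade ≤ 1 | Body of table and the rule for other immune-related reactions: discontinue permanently. Footnote: not interrupted if local skin |

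- **Grade 1:** a direct conflict on whether the dose is given.
- **Grade 2:** the text and Table 8-2 agree on holding the dose but differ on restart. The table's trigger is met only from day 7.
- **Grade 3:** up to four instructions. The footnote's wording can also be read as need not or as must not.

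**Medicated fever above 38 °C.** A treatment-related Grade 2 fever that needs medication and lasts under 7 days meets the text's skip rule but not the table's trigger. The skin footnote does not apply to fever.

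**Effect of one Grade 1 episode on dosing.** Inputs: 200 mg every 14 days; a dose delayed by more than 3 days is skipped (both Section 6.4 or 6.3); restart after more than 7 stable days.

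- Under the text, the restart condition of more than 7 days exceeds the 3-day allowance, so the dose due is lost.
- The next dose falls 14 days later. It can be given only if symptoms are relieved before day 14 − 7 = 7 after the missed dose (day 10 if the full 3-day window is used). Otherwise a second dose is lost.
- Under the table, no dose is lost.

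**Effect on the SAP exposure summary (illustration, SAP Table 3).** Take four scheduled doses with one of the middle doses skipped. Planned duration is 42 + 14 = 56 days, or 56/14 = 4 two-week units. Relative dose frequency intensity is 3/4 = 75%, below the 80% cut in SAP Section 5.4.1. At a site following the table it is 4/4 = 100%. Over 12 scheduled doses, one skip gives 11/12 = 91.7%.

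**How common rash is.** The phase I table in Protocol Section 1.7.1 lists rash in 7 subjects and maculo-papular rash in 3. Its printed percentages use 87 subjects as denominator. With full overlap, 7/87 = 8.0%. With none, (7 + 3)/87 = 11.5%.

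**The case against.** The best defence is that these are different rules for different situations. The text names rash beside wheezing, rapid breathing and suffocation, and the paragraph goes on to ruling out pneumonitis, so it could be a specific rule for a symptom cluster that overrides a general table. The sentence is badly translated: the qualifier before wheezing may extend to rash, and fever may be a joint rather than a separate condition. Table 8-2 is advisory and limited to immune-related events. The SAP tables are descriptive and will record whatever was done.

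Part of this stands. That the text applies at every grade is an inference from its silence on grade. But the protocol nowhere says that the text overrides the table, and the Grade 1 conflict lies within Section 6.4, so it does not depend on Table 8-2. A sentence that can be read in several ways is itself a reason to clarify.

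A reader might infer more than the documents support:

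- **That the Section 6.4 table also exempts Grade 3 skin events.** It does not. Its Grade 3 non-hematologic row interrupts both drugs, and its separate row for reactive capillary endothelial proliferation interrupts SHR-1210. The exemption is only in the Table 8-2 footnote.
- **That Grade 1 fever is in conflict too.** The text requires fever that needs medication. Nothing in the documents establishes that such a fever can be Grade 1, and the generic Grade 1 wording in Section 8.1.2 (for events not listed in CTCAE) describes events where treatment is not indicated.
- **That Stage I tolerability results are undermined,** because a skipped Day 15 dose would make a subject non-evaluable under Section 3.1.2. Section 3.1 has already selected the Stage II dose, and Section 3.1.2 requires at least 10 subjects per group for tolerability observation, subject to its exemption. This consequence is largely moot.
- **That the phase I rash rate, scaled to the planned enrolment, counts affected subjects.** Those are all-grade events under monotherapy, and they do not identify the grade or whether a dose was due.

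**Conclusion.** The point holds for rash at Grades 1, 2 and 3. For medicated fever it holds only for Grade 2 events shorter than 7 days. Depending on the passage followed, the same subject may be dosed, skipped or permanently discontinued.

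Per Grade 1 episode on a dosing day, the difference is at least one 200 mg dose. The number of subjects affected cannot be derived from the documents; the 8.0% to 11.5% rash rate shows only that the situation is not rare. No effect on ORR, the Stage II primary endpoint, is shown. The consequences are for consistent management of subjects, SHR-1210 exposure, and the SAP tables of events leading to SHR-1210 interruption or discontinuation.

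The conclusion assumes that rash is a trigger in its own right in the Section 6.4 text, that no grade threshold is implied, and that the rash is treatment-related so that the table applies. It should be corrected because the rules contradict each other; it is not merely a matter of missing detail.

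**What to change.** Reconcile the Section 6.4 table, the Section 6.4 paragraph on fever and rash, Table 8-2 with its footnote, and the rules for other immune-related reactions in Sections 8.7 and 9.1. One passage should govern by grade and state the trigger, the drug or drugs held, and the restart condition. The others should cross-refer to it. The rewrite should make clear whether fever and rash are separate triggers, whether causality matters, what applies to a Grade 2 event shorter than 7 days, and what the footnote's wording means.

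Check Table 9-1 at the same time. Sections 8.6 and 9.2 list fever and rash among infusion or allergic reactions, and that table continues SHR-1210 at Grade 1 and restarts at a reduced rate at Grade 2 once symptoms resolve, with no 7-day condition.

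Which rule is clinically right is for the sponsor's clinicians. The cost is a protocol clarification and a letter to sites, with no extra data or patients.
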